Patients randomized to PATH will receive their OUD treatment in the FQHC on a flexible, individualized schedule. The PATH care team – a BHC, a Peer Recovery Specialist (PRS), a Psychiatric Nurse Practitioner, and an Addictions Psychiatrist – will provide patients with an evaluation/individualized treatment plan based on the standardized needs assessment from the ASAM Criteria interview and the SAMHSA Recovery Support Services Questionnaire. The treatment plan will focus on reduction of opioid use, psychiatric stabilization, pursuit of the patient’s individual recovery goals and meeting support service needs. The course of treatment is scheduled for 1 year, with medication induction occurring in Weeks 1-4, and then transitioning to maintenance in ensuing weeks. Behavioral Treatment is most intensive in Weeks 1-13 (twice weekly), dropping to weekly for Weeks 14-26, and then as needed in Weeks 27-52. Treatment components include:

1. Medication Assisted Treatment (MAT): The medical providers will offer MAT for addiction: primarily injectable extended-release naltrexone (XR-NTX) [26,27] and office-based buprenorphine (agonist treatment) [28]. Patients will initiate these treatments in our primary care settings, in some cases participating in an ambulatory detoxification / induction on site (**OP patients**), or being inducted after an inpatient detoxification (**IP patients**). Providers will also be trained and supervised to be able to diagnose, determine treatment recommendations, initiate, and maintain outpatient psychiatric treatment per the highest tier of these specifications of the ASAM Criteria. The personalized aspect of PATH emphasizes some patient choice, with the option to pivot from one medication to another based on patient response and preference. The flexible protocol will allow opioid dependent patients to: a) remain on or taper off a long-term agonist (buprenorphine); or b) convert to antagonist (XR-NTX).

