Buprenorphine. Induction from illicit opioids onto buprenorphine will be managed by a formal protocol, developed by the federal government and which is available at: <http://www.ncbi.nlm.nih.gov/books/NBK64245/pdf/TOC.pdf>. Forms for patient and supportive significant other treatment agreements and tracking/log/patient count forms are also available online at: <http://pcssmat.org/opioid-resources/clinical-tools/#1382013035-2-36>. Drug storage and security will be managed locally at each FQHC by the facility’s pharmacy. For patients who wish to stop their buprenorphine treatment, the protocol will be used to plan patients’ gradual tapers when the patient decides to conclude maintenance therapy. Tapering patients will be offered the option of an agonist-to-antagonist transition, as current clinical thinking holds that this may ameliorate an otherwise significant rate of termination withdrawal relapse [29].

Vivitrol (XR-NTX). Patients who elect Vivitrol will first receive detoxification, as Vivitrol administration can precipitate withdrawal if given to a person who is physiologically dependent on opioids. Patients will be checked for dependence by conducting a history of recent drug use (utilizing the ASAM Criteria Software), examining the patient for fresh puncture marks and signs or symptoms of withdrawal, taking a urine drug screen, and when uncertain, conducting a naloxone challenge test. The naloxone challenge provides a good antagonist challenge that, if positive, provokes only the briefest episode of withdrawal symptoms and allows the patient to then undergo proper detoxification prior to the first Vivitrol injection. Detoxification and induction onto Vivitrol will utilize recommended protocols that have been implemented on an outpatient basis with good retention and follow-through by patients [29,30]. Detoxification will occur...

Once detoxification is established, patients will be administered the first dose of Vivitrol. Plasma concentrations of naltrexone and 6-beta naltrexol (its main metabolite) are detectable for at least 30 days after a single injection, and the medication must be re-administered to maintain its effect. Repeat doses will be scheduled 30 days (± 7 days) after the last dose, and if the patient is beyond this period, re-evaluation using the protocol above will be performed for the possibility of re-establishment of physical dependence.

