Primary Hypothesis 1: Clients in the PATH condition will demonstrate higher rates of confirmed substance abstinence (hair and UA verified) during treatment and at follow-up than clients in the SC condition. Confirmed abstinence is the “gold standard” of direct clinical outcomes in SUD research. A mixed effects logistic regression model [2,3] will be used to compare the binary outcome of hair and urinalysis-confirmed abstinence in the two treatment conditions at months 3, 6, 9, 12, 15, and 18. Mixed effects models have advantages of traditional repeated measures approaches in that they allow for missing observations, accommodate measurements made at different time points, provide flexibility in modeling the variance-covariance matrix, and permit the estimation of both group and random patient-specific effects. The model will include terms for treatment condition, time, and their interaction, and the binary baseline abstinence variable along with any other necessary covariates. We will follow the recommendations of Varadhan and Seeger [4] to test heterogeneity of treatment effect (HTE). We have identified two primary subgroup analyses to be performed: (1) setting [IP (n = 400) vs. OP (n = 400)] and (2) type of opioid [heroin (n = 534) vs. prescription (n = 266)]. We will use similar mixed effects logistic regression models (described above) that will additionally include terms for the specific subgroup variable and its interaction with treatment condition. In the event that the interaction is significant, the treatment effect will be estimated separately at each level of the categorical variable that is used to define the subgroups. In addition, we will conduct an *exploratory* subgroup analysis for medication type (agonist vs. antagonist/drug free). We anticipate simple time trends (e.g., linear or quadratic) for the mixed effects models; however, we will use linear spline models in the event complex time trends are observed, such as non-linear trends that cannot be approximated by simple polynomials in time [2]. These analyses will be performed using PROC GLIMMIX.

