Primary Hypothesis 2: Clients in the PATH condition will demonstrate greater retention in treatment than clients in the SC condition. Retention is widely considered the leading proxy for clinical effectiveness in SUD treatment. A Cox proportional hazards survival analysis [5,6] will be used to determine whether the rate of dropout differs between the two treatment conditions. The analysis will account for right-censored data as some participants may not experience the event (i.e., treatment dropout, defined as absence from treatment for 30 days) during the period of observation. The analysis will include any necessary covariates. To establish the HTE for this outcome, the survival analysis will be repeated for each primary and exploratory subgroup identified above. Models will include a term for the subgroup variable and its interaction with treatment condition. Again, if the interaction term is significant, the treatment effect will be estimated separately at each level of the categorical variable that is used to define the subgroups. We anticipate that the proportional hazard assumption will be met as we expect the typical pattern of dropout in both groups (i.e., high hazard early, low hazard late). We will conduct standard residual-based analyses to evaluate proportionality and, in the event that the

proportional hazard assumption is violated, we will use extended Cox models that include a time-dependent covariate to model the non-proportionality [7]. The analyses will be performed using PROC PHREG.

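### The exploratory medication-type subgroup is defined by treatment chosen and changed after randomisation, so its interaction test and within-level PATH vs SC contrasts are not protected by randomisation

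*SAP*

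**What the plan says.** **The subgroup.** After the two primary subgroups (setting and type of opioid), the SAP's Primary Hypothesis 1 section adds: "we will conduct an *exploratory* subgroup analysis for medication type". It has two levels, agonist and a pooled antagonist/drug-free group; the SAP's words are "subgroup analysis for medication type (agonist vs. antagonist/drug free").

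**The procedure.** Subgroup models "additionally include terms for the specific subgroup variable and its interaction with treatment condition". If the interaction is significant, "the treatment effect will be estimated separately at each level of the categorical variable that is used to define the subgroups". Under Primary Hypothesis 1 this is described just before the medication-type sentence, so its application there is the natural reading. Under Primary Hypothesis 2 it is explicit: "the survival analysis will be repeated for each primary and exploratory subgroup identified above", again with an interaction term. The secondary-outcome section plans similar subgroup analyses. The SAP's section on heterogeneity of treatment effects presents the subgroup analyses as its test of heterogeneity.

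**How medication is determined.** Protocol item 6 (PATH) schedules "medication induction occurring in Weeks 1-4". It describes patient choice, "with the option to pivot from one medication to another based on patient response and preference", and allows tapering off buprenorphine or converting to XR-NTX. On the antagonist it says "Patients who elect Vivitrol will first receive detoxification". Item 10 (risk 4) leaves the decision to participant and provider, and nobody has to take medication. In SC (item 6, Standard Care), medication comes from an intensive outpatient programme after referral, under that programme's own induction protocol. Randomisation is stratified by new/existing patient and site, not by medication.

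**The concern.** A subgroup analysis keeps the protection of randomisation only if membership is fixed before randomisation, or at least cannot be affected by the arm. Here a patient's level depends on what happens after assignment: whether the referral is completed, whether the patient stays long enough to be inducted, what patient and provider choose, and how the patient responds. These steps run through different systems in the two arms. PATH and SC patients found in the same level may then differ in prognosis, and the difference would be read as modification of the randomised effect.

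The split is also not programmable as written. The SAP does not say when medication type is measured, how switchers are classified, or where patients who leave before induction belong. The protocol's chart data on prescribed medication begin at enrolment (item 13), and item 7 lists no medication-preference item.

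At stake is a reported finding that PATH works differently by medication type, for abstinence or retention, that reflects who ended up on which medication.

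**Working it through.** The documents give no sample size, power or effect for this subgroup, so there is no planned figure to reproduce. The check asks whether the planned analysis can show an effect when PATH has none. From the SAP's power section: 25% abstinence and 60% dropout in SC, and alpha .025. From the planned enrolment: 400 per arm. Everything else is assumed, including a two-sided test and .025 for the interaction.

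**1. Abstinence model.** One binary outcome per patient; prognosis U is standard normal.
- Abstinent if ρU + √(1−ρ²)·e exceeds the 75th normal percentile (25% in each arm), with ρ = .3 to .5.
- On agonist if sU + √(1−s²)·f exceeds an arm-specific cut giving 60% uptake in PATH and 30% in SC; s is the strength of selection on prognosis.
- No arm term anywhere, so the full-sample difference is 0.

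**2. Same selection in both arms.** In the extreme case s = 1 (prognosis alone decides medication), PATH looks worse in both levels: −5.8 to −10.8 points (agonist) and −3.9 to −6.1 (other). Because both levels shift the same way, the log-odds interaction is significant in only 2.1% to 2.7% of trials, about the nominal .025. The planned condition for within-level estimates would therefore usually stop the analysis there.

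**3. Moderate selection in PATH only** (s = .5 in PATH, 0 in SC).

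| ρ | Agonist, PATH vs SC | Other level, PATH vs SC | False interaction |
|---|---|---|---|
| .3 | 28.0% vs 25.0% (+3.0) | 20.5% vs 25.0% (−4.5) | about 14% |
| .5 | 30.0% vs 25.0% (+5.0) | 17.5% vs 25.0% (−7.5) | about 38% |

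The PATH levels average back to 25%: 0.6 × 28.0 + 0.4 × 20.5 = 25.0 and 0.6 × 30.0 + 0.4 × 17.5 = 25.0. The levels now move in opposite directions, so the interaction requirement no longer protects.

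A separate logistic version (prognosis worth 1 log-odds per SD, selection 1.0 log-odds per SD, same uptake) agrees in pattern. PATH-only selection gives odds ratios of 1.30 (agonist) and 0.62 (other); equal selection in both arms gives 0.80 in both levels. If selection is unrelated to prognosis, or uptake and selection are both identical across arms, the odds ratio is about 1.00.

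**4. Retention.** Assume a constant hazard with 60% dropout by 12 months (the SAP gives no time point): λ = −ln(0.40)/12 = 0.0764 per month in both arms. If being classed as agonist requires still being in treatment at induction month t, 12-month retention among agonist patients is exp[−λ(12 − t)].
- Induction at 0.25 month in PATH and 1 month in SC: 0.41 vs 0.43; spurious Cox hazard ratio 1.10.
- Induction at 0.5 and 2 months: 0.42 vs 0.47; hazard ratio 1.21.
- Induction at 0.5 month in both, intended uptake 60% vs 30%: agonist level 1.00, other level 1.07.
- Equal timing and equal uptake: 1.00 in both levels.

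The full-sample hazard ratio is 1.00 throughout. This is immortal-time bias.

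**5. Pooling.** Suppose 40% abstinence on antagonist, 15% with no medication, and no PATH effect within either. If antagonist patients are 60% of the pooled level in PATH and 30% in SC:
- PATH: 0.6 × 40 + 0.4 × 15 = 30.0%
- SC: 0.3 × 40 + 0.7 × 15 = 22.5%
- Odds ratio: (0.300/0.700)/(0.225/0.775) = 1.48

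With 35% and 20% instead, the rates are 29.0% and 24.5%, odds ratio 1.26. With equal shares the odds ratio is 1.00, and pooling then only blurs interpretation.

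**The case against.** The strongest defence is that the analysis is labelled exploratory, carries no power claim and leaves both full-sample comparisons untouched. All of that stands, and it limits the consequence. But the label speaks to multiplicity and the weight of evidence; it does not make the compared groups comparable. The SAP's instrumental-variable and adherence analyses concern compliance and do not address this split. The optional covariates in subgroup models cannot be relied on to restore comparability lost through selection after randomisation.

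Three stronger readings are tempting and are not supported.

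- A reader might infer a high false-positive rate within each level. Testing the levels directly in the scenario of step 2 gives false significance in roughly 12% to 40% of trials per level. The SAP does not plan those tests: it requires a significant interaction first, and with that requirement the rate is at most about 1.7% per level. That scenario also lets prognosis alone decide medication.
- A reader might infer that the contrasts are necessarily biased, or would hide a true effect. They could be; whether they are depends on selection the documents do not describe. SC referral is to programmes that can provide medication treatment, and no uptake figure is given for either arm.
- A reader might treat antagonist use as a marker of early abstinence after randomisation. That does not fit the inpatient-recruited half (planned n = 400), who may be inducted following an inpatient detoxification.

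**Conclusion.** The point holds in conditional form. Medication type is settled after randomisation and by different routes in the two arms, so the interaction test and the within-level contrasts for abstinence and retention are not randomised comparisons. They are biased if selection into a level depends on prognosis and uptake or selection differs by arm. Retention adds immortal-time bias where induction requires remaining in treatment. Pooling adds bias if the antagonist/unmedicated mix differs by arm.

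No size or direction follows from the documents. The figures show only that spurious effects of several points, with a false interaction well above .025, can arise under plausible arm-specific selection, and that the interaction test stays near nominal when selection is the same in both arms. They rest on assumed uptake, selection strength and induction timing, and on one binary outcome in place of the six-visit mixed model. This is a change that should be made, but it does not threaten the primary conclusions.

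**What to change.** Remove medication type received from the heterogeneity procedure under Primary Hypotheses 1 and 2, and from the similar subgroup analyses of the secondary and exploratory outcomes. If effect modification by medication is of interest, record stated medication preference (agonist, antagonist, none) before randomisation and use that as the exploratory subgroup.

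Report medication actually received descriptively by arm, with antagonist and no medication as separate categories and with the measurement time and the handling of switchers stated. Make no PATH vs SC effect claim within those groups.

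The cost is one baseline item and a few lines of SAP text; no treatment procedure changes. The downside is that stated preference will not match medication received for every patient, so the subgroup answers a somewhat different question.

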Pilot Study: Participants enrolled in the pilot study will be assigned to receive the PATH intervention as described below. Pilot study participants will be asked to complete the following follow-up assessments: a weekly Substance Use Inventory during weeks 1 through 6, and then comprehensive follow-ups at 3 and 6 months post baseline. Assessment instruments are described below in Item 7. Pilot Study participants will be paid \$10 for completing weekly assessments and \$50 each for the 3 and 6 month follow-ups.

Main Study: Patients enrolled in the main study will be randomly assigned to one of two conditions: PATH or SC. Random assignment will be stratified by 1) whether they are a new or existing patient at the FQHC, and 2) the FQHC site where they are enrolled.

Intervention Procedures

Patients in either condition with severe SUDs with serious withdrawal complications may require detoxification, and possibly a residential stay. If we encounter more severe patients during the recruitment period, they will be referred for an inpatient stay, and allowed to present for enrollment in the study following discharge from their inpatient stay.

Standard Care

Patients randomly assigned to Standard Care will be referred to treatment at a publicly funded IOP program with MAT capability for OUD. In order to complete this referral, a BHC or PRS will meet with the patient for up to 4 brief sessions.

Participating IOPs offer dual diagnosis treatment and psychiatric medication management, and various services in case management, psychoeducation groups, and vocational rehabilitation. Each program has an MAT induction protocol that is offered in greater intensity in the first weeks of treatment; once a patient is stabilized and demonstrating abstinence, they can then attend fewer medication management visits. IOP programming consists of nine hours of group (typically delivered in three three-hour blocks) and one hour of individual. All of these programs strive to integrate ESTs and 12-Step as a cornerstone to their approach. IOPs typically last 3-4 months, and then step down to outpatient management, which is typically 3 hours per week for up to 9 months, and as needed after that. Patients assigned to SC will still receive primary care at the FQHC.

PATH

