Medication Support. Patients receiving either medication will be given initial and ongoing support to increase understanding of the role of medicine (e.g., foundational and stabilizing, but requiring psychosocial treatment), the medication options, and differences in side effects and risks. Periodic re-evaluation will examine with the patient his/her progress towards goals and, in the event of less than anticipated progress, review the contingency plan (e.g., medication or dose changes, co-occurring disorder management, and escalation of recovery support).

2. Cognitive-Behavioral / Relapse Prevention with Contingency Management: The BHC will deliver manualized cognitive-behavioral relapse prevention (CB/RP) along with contingency management (CM). During Weeks 1-13, patients in the PATH condition will come to the FQHC twice per week for CM and CB/RP sessions. CB/RP will then continue with once weekly sessions in Weeks 14-26, and as needed but tapering in frequency for Weeks 27-52. Procedures for CM and CB/RP are as follows:

Urine Sample Collection and Testing. Patients will be scheduled to provide urine samples twice weekly prior to seeing the LCSW for their regular counseling visits, which will be separated by 2 or 3 days. Samples will be collected under direct observation by a same-sex staff member. Valid samples will be tested for Opioids using quick read test strips at the cutoff levels established by SAMHSA to indicate substance abstinence (specific testing materials to be determined by the FQHC's billing and reimbursement practices). Urinalysis results will be entered into a database that calculates the value of the voucher to be delivered.

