3. Recovery Support Services: Peer Recovery Specialists will work with the BHC to aid the patient in social service needs, help patients stay motivated and connected and begin focusing on personal recovery goals. Patients will set goals with the Peer Specialist and professional SUD treatment team to improve housing and employment, family / social functioning, manage child care, develop supportive relationships and establish a daily routine. The Peer Recovery Specialist will help the patient access community resources, and offer longitudinal peer / relational support. The Peer Recovery Specialist also provides a model of a recovery lifestyle. If a patient goes missing, the Peer Specialist will seek out the patient by telephone or through contacts and re-engage them.

Follow-up Procedures

We will complete follow-up assessment interviews with participants at 3-, 6-, 9-, 12-, 15- and 18-months post-baseline. Follow-up assessments will take place in-person, generally at the FQHC site. If the participant is not able to travel to the FQHC (or they have been discharged and are not allowed back on the premises), then we will meet them in a safe, neutral location such as a restaurant or public library. The assessment battery will be similar to that collected at Baseline (see Item #7), and we will collect a hair and urine sample. If a participant is incarcerated at any follow-up point research staff will not attempt to contact the participant while incarcerated.

We will also call participants every month that a follow-up assessment is not due (i.e. months 1, 2, 4, 5, 7, 8, 10, 11, 13, 14, 16, and 17) to verify the Locator information they provided at baseline, and update any information that has changed.

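### The 30-day dropout event for Primary Hypothesis 2 conflicts with the protocol's own schedule: patients on a permitted injection interval, or who finish care as planned, can be scored as dropouts

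*SAP*

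**What the plan says.** **The event.** SAP, Primary Hypothesis 2, defines it as "treatment dropout, defined as absence from treatment for 30 days". Patients without the event in the period of observation are censored. That section gives the period no length, does not define treatment, and has no rule for completing care.

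**Data source.** Protocol item 7 (Case Review) takes engagement data first from funders' payment records and settles disagreements with patient report by chart review. Item 7 (Chart Review) lists session attendance, prescriptions filled and doses received. No rule combines them into retention.

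**PATH schedule (item 6).** XR-NTX and buprenorphine are the two main medications offered. For XR-NTX: "Repeat doses will be scheduled 30 days (± 7 days) after the last dose, and if the patient is beyond this period, re-evaluation" is called for. Behavioural treatment is twice weekly in Weeks 1-13, "dropping to weekly for Weeks 14-26, and then as needed in Weeks 27-52"; the counselling subsection says "as needed but tapering in frequency for Weeks 27-52". Medication support is ongoing and peer specialists "offer longitudinal peer / relational support", both without a stated frequency. "The course of treatment is scheduled for 1 year".

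**Standard Care (SC) schedule (item 6).** The intensive programme typically lasts 3-4 months, followed by step-down care for up to 9 months and then care as needed. On medication, "once a patient is stabilized and demonstrating abstinence, they can then attend fewer medication management visits".

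**Duration.** Aim 3 (item 2) describes an 18-month trial. Follow-up interviews (item 6) and the engagement statement (item 10) also run to 18 months, and chart collection (item 13) runs to the end of each patient's involvement.

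**Power.** The SAP assumes 60% dropout in SC, with no time attached.

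**The concern.** Applied literally, the event definition can count as dropouts two kinds of patient who are following the plan.

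- **Dosing gap.** A patient whose next injection falls on day 31 to 37 is inside the protocol's window. If retention is measured by visits or bills and nothing else is counted in between, that patient has been absent for 30 days.
- **Planned completion.** A patient who finishes the 1-year PATH course, or whose SC step-down care ends as intended, stops attending inside an 18-month trial. Thirty days later the definition is met.

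This is the event for one of two primary hypotheses. Two analysts working from the same charts could derive different events, and the choice could be made after the data are seen. False events unrelated to treatment pull the hazard ratio towards 1. False events concentrated in one arm bias the comparison.

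**Working it through.** **1. The plan's own figure.** Inputs (SAP, Power for the Primary Hypotheses): n = 800, HR .74, SC dropout 60%, alpha .025. Two-sided alpha is assumed because it is what reproduces the 80%. Allocation is 400 per arm (protocol item 4).

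- PATH event-free share: .40^.74 = .508, so PATH dropout is .492.
- Expected events: 400 × (.60 + .492) = 437.
- Events needed (Schoenfeld): 4 × (2.241 + .842)² / (ln .74)² = 419.
- Power: Φ(√437 / 2 × .301 − 2.241) = Φ(.906) = 82%.

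The figure reproduces.

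**2. The dosing gap.** The permitted interval is 30 − 7 = 23 to 30 + 7 = 37 days. An interval of 31 days or more leaves at least 30 full days without a visit. Weeks 1-26 are protected by weekly or twice-weekly sessions. Weeks 27-52 are 182 days, or 182/30 ≈ 6 intervals. If a share p of intervals exceeds 30 days and there is no other contact, the chance of at least one such gap is 1 − (1 − p)^6:

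- p = 5%: 26%
- p = 10%: 47%
- p = 20%: 74%
- whole-day intervals uniform over 23-37 days, p = 7/15: 98%

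Other contacts cut this quickly. In simulation with random contacts:

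| Intervals over 30 days | 0 contacts per 30 days | 1 | 2 | about weekly |
|---|---|---|---|---|
| 5% | 27% | 12% | 5% | 1% |
| 10% | 47% | 22% | 9% | 1% |
| 20% | 74% | 40% | 18% | 2% |
| uniform 23-37 days | 98% | 69% | 35% | 5% |

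The protocol gives neither p nor the contact frequency. A 30-day target with a tolerance does not imply uniform intervals, so the last row is an extreme.

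**3. Effect of false dropouts on power (assumed inputs).** 400 per arm; Weibull dropout with shape .6; 60% SC dropout by week 52; true HR .74; false events spread over Weeks 27-52. The flagged share is of patients still in care at week 26.

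| Wrongly flagged, PATH / SC | Power |
|---|---|
| 0 / 0 | 81% |
| 5% / 5% | 79% |
| 10% / 10% | 77% |
| 2% / 0 | 75% |
| 5% / 0 | about 64% |
| 10% / 5% | about 61% |
| 10% / 0 | about 43% |

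The unequal rows depend on an imbalance that the documents neither establish nor exclude.

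**4. Planned completion.** SC scheduled care lasts 3-4 months plus up to 9, so up to 12-13 months. PATH lasts 12. Both end inside 18 months. Assume dropout as in step 1 by week 52, and that everyone then still in care finishes around week 52 and is scored as an event. This is the worst case, because some will continue in as-needed care. The extra events number 800 − 437 = 363 and carry no treatment information.

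- Signal: 437 × .301 / 4 = 32.9.
- Information: 800 / 4 = 200.
- Z: 32.9 / √200 = 2.33, so power is Φ(2.33 − 2.241) ≈ 53%.
- Apparent HR: exp(−32.9 / 200) = .85, against a true .74.

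Simulation under the same assumption gives about 55%, against 81% without the false events.

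**5. A one-sided remedy.** The protocol states a dosing window only for XR-NTX under PATH. With no true effect, 25% of both arms seen at injections plus one other contact per 30 days, and the allowance given to PATH only, simulated false PATH wins were 4.1% (10% of intervals over 30 days) and 29% (uniform intervals), against a nominal 1.25%. With the same allowance in both arms they were about 1%.

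**The case against.** The event is absence from treatment, not from visits. A patient inside the dosing window is on the protocol's treatment schedule, and the SAP's sensitivity section treats medication as a component of the intervention. On that reading the first conflict disappears. This is a sensible reading, but the SAP does not adopt it, and billing records are the first data source. The gap also requires XR-NTX, Weeks 27-52 and no other counted contact for more than 30 days. Medication support and peer outreach make that less likely, by an amount that cannot be stated.

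The SAP also plans sensitivity analyses with other outcome definitions and a check of proportional hazards. Neither fixes the primary event.

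Two stronger readings are tempting. A reader might infer that the observation period is wholly undefined. It is not: Aim 3 sets Primary Hypothesis 2 within an 18-month trial, and follow-up and the engagement statement agree. What is missing is a horizon in the SAP and a rule for patients whose planned care ends before it. A reader might also infer that the definition works against PATH. The documents do not support that: SC also moves stable patients to fewer medication visits and later to as-needed care, and its medication mix is not given.

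**Conclusion.** The conflict stands and should be fixed before analysis. A literal 30-day absence rule can score as dropouts both patients on a permitted injection interval and patients who finish care as planned. This conclusion needs only the documents' own schedules.

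Its size and direction are unknown. The illustrations rest on assumed contact patterns, dropout shape and completion timing. Within them, equal misclassification costs about 2 to 4 points of power (81% to 79% or 77%), misclassification mainly in PATH costs much more, and scoring completers in both arms costs about 26 points (81% to about 55%). The low power values under PATH-only misclassification are conditional examples, not forecasts. Nor do they show that the sponsor's power calculation is wrong: it reproduces, though its 60% dropout rate needs a time point.

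**What to change.** Change the SAP only; care schedules stay as they are. Reconcile Primary Hypothesis 2 with protocol item 6 (PATH schedule and dosing window), item 2 (Aim 3), item 10 and item 13.

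1. In both arms, count any attended opioid use disorder treatment contact or recorded dose as treatment, from one list that also says whether a filled prescription counts.
2. Do not score a dropout for a gap that the protocol's own dosing schedule permits. Apply the same numerical allowance to both arms, because an allowance for PATH alone would favour PATH.
3. State one common horizon and attach the 60% dropout assumption to it. Censor documented planned completion, using the discharge status collected under item 13, and report completions by arm.
4. State one rule for dating the event, the same in both arms.
5. Keep the flat 30-day rule as a sensitivity analysis and report by arm how many events change.

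**Cost.** SAP wording and extra derivation. Attendance, doses received, prescriptions filled and discharge status are already listed for collection. Dropout is recognised slightly later. Censoring completers assumes that completion is unrelated to later dropout risk, and the SAP should say so.
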